10.2 Baseline Values

Unless otherwise noted, baseline is defined as the last non-missing value recorded prior to the first dose of study drug. Unscheduled visits will be used in the determination of baseline values, when applicable.

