5.5 Criteria for Temporarily Delaying Enrollment and Administration of Trial Intervention

Each child may have their dosing visit rescheduled within the visit window for Visit 2 with an additional 21 days compared to Visit 1 (thus the maximum time interval between Visit 1 and Visit 2 will be 50 days + 21 days) due to the following circumstances:

- If the patient has taken any prohibited medication prior to the dosing visit (Visit 2)
- If transient illness means that the patient cannot attend the planned dosing visit (Visit 2)
- If the patient cannot attend the planned dosing visit (Visit 2) due to logistical reasons
- If the target plasma glucose cannot be achieved on the dosing day (Visit 2) while inducing hypoglycemia

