At the discretion of the investigator, additional plasma glucose measurements can be taken at any time during the trial, for example when there is a suspicion (eg, symptoms) of a hypoglycemic episode.

A catheter (eg, an indwelling catheter) will be inserted into the child's arm for blood draw for PK/PD sampling. If possible, the same IV access as used for insulin infusion can be used for the PK/PD sampling to reduce the stress and discomfort for the child. Attention should be made to ensure blood samples will be collected from the circulating blood volume and not from a reservoir dead space created by the catheter. If direct venipunctures are considered more appropriate, especially for those children where the number of PK and PD samples are reduced (refer to Table 6-4), venipunctures can be used instead of indwelling catheters. The catheter will be placed in the morning prior to IMP administration. Blood samples for baseline assessment of plasma glucose and dasiglucagon PK will be collected approximately 5 minutes after the glucose concentration reaches >70 mg/dL and < 90 mg/dL (3.9 to 5.0 mmol/L). These samples are the baseline samples and should be collected within 2 minutes before IMP administration. The baseline samples will be sent to the clinical laboratory and analyzed using a sensitive and validated assay for glucose measurements. The assay used for primary endpoint glucose measurements should fulfil the requirements of the US FDA Bioanalytical Method Validation Guidance for Industry Section 5 B and C for biomarkers. ⁶ The sampling procedure is described in Section 6.5.3. Before IMP administration, it must be confirmed by the glucose analyzer that the plasma glucose is still ≥70 mg/dL and <90 mg/dL.

If plasma glucose is < 70 mg/dL (3.9 mmol/L), IV glucose solution will be administered to raise plasma glucose to within the 70 to 90 mg/dL (3.9 to 5.0 mmol/L) target range. The run-in period will be adequately extended (at least 30 minutes) until the above target is achieved, the glucose infusion has been discontinued, and new baseline samples for plasma glucose will be collected. In this case, glucose should not be infused within 30 minutes before IMP administration. If plasma glucose is not within the target range after the second attempt, the patient should be rescheduled for a new treatment visit within 7 days (+2 days).

Insulin-Induced Hypoglycemia and Dosing Figure 6-1

Abbreviations: IV=intravenous; PG=plasma glucose

Zealand Pharma A/S

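### Does the SAP's last-value-before-dosing rule let the glucose baseline depart from the protocol's laboratory pre-dose sample?

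*SAP*

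**What the plan says.** SAP section 10.2 has two sentences that apply to all variables. The first is "Unless otherwise noted, baseline is defined as the last non-missing value recorded prior to the first dose of study drug". The second is "Unscheduled visits will be used in the determination of baseline values, when applicable". The footnotes to Table 14.2.1.1 (30 minutes, primary) and Table 14.2.2.1 (15 minutes, secondary) repeat the last-value rule, with no special provision for glucose.

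Protocol section 6.5.1 is more specific. Of the glucose and PK samples drawn once glucose is in the target range, it says "These samples are the baseline samples and should be collected within 2 minutes before IMP administration" and "The baseline samples will be sent to the clinical laboratory and analyzed using a sensitive and validated assay for glucose measurements". It also requires an on-site check: "Before IMP administration, it must be confirmed by the glucose analyzer that the plasma glucose is still" within the 70 to 90 mg/dL range. For a child who drops too low, "If plasma glucose is < 70 mg/dL (3.9 mmol/L), IV glucose solution will be administered", the run-in is extended, and "new baseline samples for plasma glucose will be collected".

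Protocol section 5.5 allows the dosing visit to be rescheduled, one listed reason being "If the target plasma glucose cannot be achieved on the dosing day (Visit 2) while inducing hypoglycemia".

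SAP section 11.3 plans a sensitivity analysis with the nominal pre-dose time point as baseline (Tables 14.2.3.6 to 14.2.3.8). SAP section 15 declares no change from the protocol's analyses.

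**The concern.** The protocol ties the baseline to one assay and a 2-minute window, and the SAP ties it only to order in time. The SAP also treats the two as separable: it plans a second analysis on the nominal pre-dose value, and Listing 16.2.6.1 prints both changes where they differ.

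Two routes to a wrong baseline suggest themselves.

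1. The final laboratory sample is missing, and the rule falls back to an older one, taken before run-in glucose or at an abandoned dosing attempt.
2. The analyzer reading that clears the child for dosing is the latest glucose record, so it displaces the laboratory value.

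Either way, a laboratory value after dosing would be compared with a baseline from another device or another glycemic state. The error enters the child's change one for one. Each dose group has 4 children, so one child carries a quarter of the mean, and Protocol section 4.3 says the results will be used to choose the dose or doses for this age group.

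**Working it through.** **The plan's own figure.** SAP section 5 states that 8 children give a 95% interval of ±25 mg/dL with 95% probability at SD 20. The probability that the half-width is at most 25 is the chi-square distribution function with n−1 degrees of freedom at (n−1) × [25√n / (t × 20)]².

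- n = 8: 7 × [25 × 2.828 / (2.365 × 20)]² = 15.65, probability 0.972.
- n = 7: probability 0.910.

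Eight is the smallest number that reaches 0.95. The figure reproduces and does not depend on the baseline rule.

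**Which value the rule selects.**

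- *Visit.* SAP section 13 bases the primary and secondary glucose endpoints on samples from Visit 2. In Protocol Table 1-1, plasma glucose is scheduled only at Visit 2. The one unscheduled visit in that table is for antibody-positive children and comes after Visit 3 (Protocol section 8.1.3). The unscheduled-visit sentence in SAP 10.2 therefore has nothing to act on for glucose before dosing.
- *Assay.* Protocol section 8.5 sends the efficacy glucose samples to the clinical laboratory. Analyzer data have their own section (SAP 14.10), figure (14.3.6.2) and listing (16.2.5.9). Listing 16.2.6.1, which holds the efficacy glucose values, puts the baseline flag on the pre-dose sample.
- *Order.* Protocol sections 8.1.2 and 8.5 place an analyzer confirmation before the pre-dose PK and PD samples as well as before dosing. With that order, the laboratory sample comes after the reading.
- *Repeated run-in.* Two pre-dose laboratory samples may exist. The last-value rule takes the second, as the protocol intends. A rule naming only the nominal pre-dose sample could be ambiguous here.
- *Abandoned visit.* Baseline samples are drawn about 5 minutes after glucose reaches the target range. A visit abandoned because the target was never reached would often have no such sample.

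What remains is a double exception: the final laboratory sample is missing, and an earlier one from a first run-in or a previous attempt exists.

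**Size in that exception.** A difference d in one child moves a 4-child mean by d/4 and the 8-child mean by d/8. If both values lie in the 70 to 90 window, d is at most 90 − 70 = 20 mg/dL. This is an assumption for scale, not an estimate.

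| | 4 children | 8 children |
|---|---|---|
| Shift at d = 20 | 20/4 = 5.0 | 20/8 = 2.5 |
| Expected half-width, t × 20/√n | 3.182 × 20/√4 = 31.8 | 2.365 × 20/√8 = 16.7 |
| Ratio | 16% | 15% |

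A value from early in the induction could differ more. An assumed d of 60 to 110 gives 15 to 27.5 mg/dL (4 children) and 7.5 to 13.8 mg/dL (8 children). The protocol schedules no laboratory baseline draw that early, so this case requires analyzer readings to enter the efficacy data.

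**Cost of a strict rule.** If only a laboratory sample from the dosing occasion counted, a child without one would leave the main table, because SAP section 10.4 allows no imputation. A dose group of 3 has an expected half-width of 4.303 × 20/√3 = 49.7 mg/dL, against 31.8 with 4. Over all children, going from 8 to 7 widens it from 16.7 to 18.5.

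**The case for a change.** The best case for a change is that this is the primary endpoint, the groups are very small, and one sentence plus two footnotes would remove the doubt without new data. No text expressly bars an analyzer value. Protocol section 8.5 asks for baseline glucose to be entered in the eCRF in the same paragraph as the analyzer reading, and Listing 16.2.5.5 carries a confirmatory glucose value. The order of readings in sections 8.1.2 and 8.5 does not exclude another analyzer check after the laboratory draw. An abandoned attempt might also keep the Visit 2 label, so SAP section 13 does not fully close that route. Finally, a sensitivity analysis reveals a discrepancy but does not decide which result is primary.

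Each of these stands as a remark on wording. None shows that an analyst following the plan would choose a different value when the laboratory sample exists. No direction of bias is established either: a sample from before run-in glucose might lower the baseline and overstate the rise, while an early-induction value would do the reverse. An earlier laboratory sample taken in the target range need not be below 70 mg/dL at all.

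Nor is the stricter rule a clear gain. It alters the result only in the rare double exception, where it trades a possible shift of about 5 mg/dL for the loss of a child and a half-width wider by 49.7 − 31.8 = 17.9 mg/dL in that dose group. Bias and imprecision are not the same currency, and a statistician could reasonably prefer either.

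**Conclusion.** No change follows. The baseline rule is a generic sentence that analysts will apply sensibly, because SAP section 13, Protocol sections 6.5.1 and 8.5, and the separate analyzer outputs all point to the laboratory pre-dose sample at the dosing visit. When that sample is present and is the last laboratory glucose before dosing, the SAP and protocol baselines are identical and the effect is zero.

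In the residual exception, the shift is 5.0 mg/dL in a dose group and 2.5 mg/dL overall per affected child. This assumes a 20 mg/dL difference, an SD of 20 mg/dL carried over from the earlier trial in children aged 6 to 11 years, and full groups of 4. The documents give no frequency for the exception.

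Any such case would also be visible. Listing 16.2.6.1 shows both changes for each child where they differ, the sensitivity tables repeat the endpoint on the nominal pre-dose value, and Protocol section 10.1.6 treats a missing primary endpoint as a major deviation for review before the data are released. With 8 children fully listed and no hypothesis test, a reader could see and judge the effect directly. Naming the assay in SAP 10.2 would be harmless tidying and is not needed for a sound analysis.

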10.3 Adjustments for Covariates

No adjustments for covariates will be made.

10.4 Handling of Dropouts or Missing Data

No imputations will be made for missing values. Summaries will be based on observed data only. For handling of PK concentrations and results BLOQ, please refer to section 0

10.5 Interim Analysis and Data Monitoring

No interim analysis is planned for this study.

Data monitoring will be completed by the Trial Safety Group. New patients will only be dosed after safety assessment of the dosing visit for the preceding patient is completed and assessed by the Trial Safety Group. Thus, except for the first patient being dosed in the trial, investigators need written permission (eg, via an email) from the TSG chair to dose a patient in the trial.

More information on the TSG is available in the protocol.

10.6 Examination of Subgroups

No subgroup analysis is planned for this study.

10.7 Multiple Comparison/Multiplicity

No adjustments for multiplicity will be made in this study.

10.8 Multicenter Studies

This is a multicenter study with 8 subjects to be treated.

The expected low number of subjects per centers does not allow to do subgroup analysis within each site or to stratify by center.

11. METHODS OF EFFICACY ANALYSIS

11.1 Primary Efficacy Analyses

The primary efficacy endpoint, plasma glucose change from baseline at 30 minutes after trial product injection or at the time of rescue by IV glucose if before 30 minutes, will be summarized using descriptive statistics and 95% confidence intervals (based on a *t* distribution).

11.2 Secondary Efficacy Analyses

The secondary efficacy endpoint, plasma glucose change from baseline at 15 minutes after IMP injection or at the time of rescue by IV glucose if before 15 minutes, will be summarized using descriptive statistics.

11.3 Further Efficacy Analyses

Untransformed and change from baseline plasma glucose at all timepoints , will be summarized using descriptive statistics.

A plot of mean glucose concentrations (untransformed) versus each time point will be provide and presented with error bars representing the Standard error of means (SEM).

A overlay plot of individual glucose concentrations (untransformed) versus each time point will be created.

A sensitivity analysis will be performed using the nominal pre-dose time point as baseline instead of the last valid measurement prior dosing.

12. PHARMACOKINETIC ANALYSES

The pharmacokinetic analysis will be based on the PAS set.

12.1 Pharmacokinetic Variables

The following PK parameters for the dasiglucagon plasma concentrations will be estimated by non-compartmental analysis (NCA):

| PK parameter abbreviation | PK parameter | Calculation |
|---------------------------|--|---|
| AUC _{0-30min} | Area under the plasma concentration versus time curve (AUC) from 0 to 30 minutes post-dose | Linear trapezoidal rule for the ascending part of the concentration-time curve, logarithmic trapezoidal rule for the descending part. |

| PK parameter abbreviation | PK parameter | Calculation |
|---------------------------|---|--|
| AUC _{0-300min} | AUC from 0 to 300 minutes post-dose | Linear trapezoidal rule for the ascending part of the concentration-time curve, logarithmic trapezoidal rule for the descending part. |
| AUC _{0-t} | AUC from 0 to the last time point with a measured concentration | Linear trapezoidal rule for the ascending part of the concentration-time curve, logarithmic trapezoidal rule for the descending part. |
| AUC _{0-inf} | AUC from 0 to infinity post-dose | (AUClast + Clast _{obs}) / λ _z , where Clast _{obs} is the concentration corresponding to Tlast (time of last measurable (positive) concentration). |
| C _{max} | Maximum observed concentration | Taken directly from analytical data, selected from individual concentration data. The time when the first occurrence of Cmax is taken as Tmax. |
| T _{max} | Time to C _{max} | Taken directly from analytical data, selected from individual concentration data |
| λ _z | Terminal elimination rate constant of plasma dasiglucagon | Calculated by linear regression of the terminal linear portion of the log concentration vs. time curve. At least 3 concentrations in the terminal elimination phase will be required to calculate λ _z . |
| t _½ | Terminal plasma elimination half-life of dasiglucagon | Ln(2) / λ _z |
| CL/f | Total body clearance of plasma dasiglucagon | Dose / AUC _{0-inf} |
| Vz/f | Volume of distribution of plasma dasiglucagon | Dose / (λ _z * AUC _{0-inf}) or CL/f / λ _z |
| MRT | Mean residence time of plasma dasiglucagon | AUMC _{inf} / AUC _{0-inf} where AUMC _{inf} is the area under the first moment curve as estimated by WinNonlin. |

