6. GENERAL ANALYSIS CONSIDERATIONS

The statistical analyses will be reported using TLFs. The International Council for Harmonisation of Technical Requirements for Pharmaceuticals for Human Use (ICH) numbering convention will be used for all TLFs.

Continuous variables will be summarized by presenting the number of observations, means, SDs, medians, minimums, and maximums. In addition, 95% confidence intervals (based on a *t* distribution if not otherwise stated) will be calculated if appropriate and detailed in the table shells. For logarithm-transformed data (relevant for selected PK summaries), the geometric mean and coefficient of variation % will also be provided.

Categorical variables will be summarized by presenting counts and percentages of subjects in corresponding categories. All possible categories as defined in the CRF should be populated, even if they have zero counts. Percentages for missing values are omitted and do not account for the percent calculation of other categories. Percentages are based on the total category count excluding the missing category if not otherwise mentioned. In certain tables (eg, AEs), the total number of subjects is used as the denominator. Footnotes will specify the percent basis in those cases.

All data collected in this trial and documented in the eCRFs will be presented in data listings. In case of termination of the trial, all data collected up to that time point will be included in the analysis.

All summary tables will be presented for the two treatment groups and total.

Individual subject data obtained from the eCRFs, external vendors, central clinical laboratory, central ECG laboratory, PK data, and any derived data will be presented by subject in data listings.

The analyses described in this plan are considered a priori, in that they have been defined before first patient dosed in the study. Any analyses performed after first patient dosed will be considered post hoc and exploratory. Post hoc analyses will be labeled as such on the output and identified in the CSR.

All analyses and tabulations will be performed using SAS® statistical software, version 9.4 or higher (SAS Institute Inc., Cary, North Carolina, USA). PK and PD analyses will be performed using Phoenix® WinNonlin®, version 8.3.4 or higher (Certara USA, Inc., Princeton, New Jersey, USA). This software was validated by Syneos Health in compliance with US 21 CFR Part 11 Regulation.

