12.4 Determination and Analysis of Pharmacokinetic Parameters

Full precision concentration data and actual sample times will be used for the determination of all PK parameters.

Raw plasma concentrations for the derivation of PK parameters will be handled as described in Section 12.1.

The PK parameters as listed in Section 12.1 will be estimated.

Reporting of missing PK parameters:

The percentage of extrapolated AUC should not exceed 20% of AUC_{inf} for each individual profile. If the percentage of extrapolated AUC is more than 20%, the individual AUC_{inf} result and parameters depending on AUC_{inf} will be listed but flagged as not reliably calculated. They will generally not be included in descriptive statistics and statistical testing procedures.

The terminal half-life regression analysis should contain data from at least 3 different time points after C_{max} in the terminal phase and as many data points as possible (always including the last quantifiable concentration but excluding the concentration at T_{max}), consistent with the assessment of a straight line on the log-transformed scale. The coefficient of regression (r^2) should be larger than or equal to 0.80. If at least one of these conditions is not fulfilled, the terminal half-life and parameters depending on $t_{1/2}$ will be listed but flagged as not reliably calculated. They will generally be excluded from descriptive statistics and statistical testing procedures. However, if the reliability of the estimated terminal half-life is judged to be reasonable by the pharmacokineticist who oversees the PK analysis, the $t_{1/2}$ and related parameters would not be excluded.

Individual PK parameters:

A raw data listing will be provided displaying the individual PK parameters. Results will be displayed using 3 significant digits.

Summary statistics of PK parameters:

Pharmacokinetic parameters will be summarized using descriptive statistics (n, arithmetic mean, SD, CV% for the arithmetic mean, median, minimum, maximum, geometric mean, and CV% for the geometric mean). The geometric mean and CV% for the geometric mean will not be calculated for T_{max} . Results will be displayed using 3 significant digits.

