| Statistic | Cmax (pmol/L) | Tmax (h) | Lambda z (1/h) | T1/2 (h) | AUC (0- 30mins) (unit) | AUC (0-300) (unit) | AUC (0-tlast) (unit) | AUC (0-inf) (unit) | CL/f (unit) | Vz/f (unit) | MRT (unit) |
|--------------------------------------|------------------|-------------|-------------------|-------------|---------------------------------|--------------------------|----------------------------|--------------------------|----------------|----------------|---------------|
| n | xx | xx | xx | xx | xx | xx | xx | xx | xx | xx | xx |
| | xx.x | xx.x | xx.x | xx.x | xx.x | xx.x | xx.x | xx.x | xx.x | xx.x | xx.x |
| Mean (SD) | (xx.xx) | (xx.xx) | (xx.xx) | (xx.xx) | (xx.xx) | (xx.xx) | (xx.xx) | (xx.xx) | (xx.xx) | (xx.xx) | (xx.xx) |
| Mean CV (%) | xx.x | xx.x | xx.x | xx.x | xx.x | xx.x | xx.x | xx.x | xx.x | xx.x | xx.x |
| Median | xx.x | xx.x | xx.x | xx.x | xx.x | xx.x | xx.x | xx.x | xx.x | xx.x | xx.x |
| Min, Max | xx.x | xx.x | xx.x | xx.x | xx.x | xx.x | xx.x | xx.x | xx.x | xx.x | xx.x |
| Geometric Mean | xx, xx | - | xx, xx | xx, xx | xx, xx | xx, xx | xx, xx | xx, xx | xx, xx | xx, xx | xx, xx |
| Geometric Mean CV (%) ^[a] | xx.x | - | xx.x | xx.x | xx.x | xx.x | xx.x | xx.x | xx.x | xx.x | xx.x |

Results are displayed to 3 significant digits.

^[a] Geometric CV (%) is calculated as $[\exp(\text{SD}^2) - 1]^{1/2} * 100$, where SD is standard deviation of the natural-log transformed data.

Source: xxx

PROGRAM SOURCE: xxx.sas, DATA CUT-OFF DATE: DDMMYYYY

RUN DATE: DDMMYYYY hh:mm

Programming note:

- 1) Extend to a 2nd page if not sufficient space to display full length of numbers
- 2) Order PK parameters per the order in Section 12.1 of the SAP.
- 3) The geometric mean and CV% for the geometric mean will not be calculated for T_{max}

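### SAP 12.1 divides the whole of (AUClast + Clast) by λz to get AUC0-inf; only Clast should be divided, and CL/f, Vz/f and MRT inherit the error

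*SAP*

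**What the plan says.** SAP 12.1 lists eleven PK parameters to be estimated by non-compartmental analysis, each with a calculation. For the row described as "AUC from 0 to infinity post-dose" the calculation is "AUClast + Clast _{obs}) / λ"z. The opening bracket stands before AUClast and the closing bracket after Clast. The row then defines the second term: it "is the concentration corresponding to Tlast (time of last measurable (positive) concentration").

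Three later rows use the result:
- CL/f: "Total body clearance of plasma dasiglucagon | Dose / AUC"0-inf.
- Vz/f: dose over the product of λz and AUC0-inf, or equivalently CL/f over λz.
- MRT: AUMCinf over AUC0-inf, with AUMCinf taken from WinNonlin.

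SAP 12.4 sets a reliability rule: "The percentage of extrapolated AUC should not exceed 20% of" AUCinf in any individual profile. Results that break it are flagged and generally left out of the summaries. SAP 6 names the software: "PK and PD analyses will be performed using Phoenix" WinNonlin. Protocol 8.4 and 9.4.3.2 name AUCinf but give no formula, and no other section of the SAP gives a different one.

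**The concern.** AUC0-inf is the observed area plus an extrapolated tail. Only the tail involves λz, because a mono-exponential decline from Clast has area Clast/λz. The printed rule puts AUClast under the same divisor. The 20% rule in 12.4 makes sense only if AUCinf contains AUClast as a part, so the SAP's own reliability rule does not fit its own formula.

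AUCinf, CL/f, Vz/f and MRT are listed PK endpoints (Protocol 3), and Protocol 4.3 says the trial results will be used to determine the dose or doses for children under 6. With four children planned per dose, a systematic error in the individual values passes straight into the group summaries. SAP 1 says that deviations from the plan will be documented in the CSR, so even a correct software value would formally depart from the plan as written.

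**Working it through.** **1. Units.** AUClast is concentration × time, Clast is concentration, and λz is 1/time.
- Correct form, AUClast + Clast/λz: both terms are concentration × time.
- Printed form, (AUClast + Clast)/λz: the bracket adds concentration × time to concentration. After division, the first term is concentration × time² and the second is concentration × time.

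The printed form is therefore not an AUC, whatever the data. Its size relative to the correct value also changes with the time unit. The two agree only when λz is numerically 1; in hours that is a half-life of 60 × ln 2 = 41.6 min.

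**2. Size, worked example.** The documents give no AUC, Clast or half-life for these children, so there is no plan figure to reproduce. Assumptions: AUClast 1000 pmol·h/L, Clast 10 pmol/L, terminal half-life 20 to 60 min. Time is in hours because the shell of Table 14.2.4.7 gives Tmax and half-life in h and λz in 1/h. λz = ln 2 / half-life.

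| Half-life (min) | λz (1/h) | Correct: 1000 + 10/λz | Printed: 1010/λz | Printed/correct | CL/f, Vz/f, MRT multiplied by |
|---|---|---|---|---|---|
| 20 | 2.079 | 1004.8 | 485.7 | 0.48 | 2.07 |
| 30 | 1.386 | 1007.2 | 728.6 | 0.72 | 1.38 |
| 40 | 1.040 | 1009.6 | 971.4 | 0.96 | 1.04 |
| 60 | 0.693 | 1014.4 | 1457.1 | 1.44 | 0.70 |

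At 20, 30 and 40 min the printed AUC0-inf is below AUClast, which is impossible.

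**3. Sensitivity to the assumed areas.** With AUClast from 500 to 10,000 and Clast from 1 to 50, still in hours, the ratio is 0.48 to 0.51 at 20 min and 1.39 to 1.44 at 60 min. It stays close to 1/λz because the tail is small.

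**4. Simulated profiles and the time unit.** This check used the SAP sampling times for children above 10 kg, linear-up/log-down trapezoids as in 12.1, and an assumed one-compartment shape with an 8 min absorption half-life.

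| Half-life (min) | Printed/correct, hours | Printed/correct, minutes |
|---|---|---|
| 20 | 0.48 | 29 |
| 30 | 0.72 | 43 |
| 45 | 1.08 | 64 |
| 60 | 1.43 | 83 |

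**5. Dependent parameters.** CL/f and MRT change by the inverse ratio. In the simulated 30 min case, MRT goes from 0.93 h to 1.29 h. For Vz/f, Dose/(λz × printed AUC0-inf) reduces to Dose/(AUClast + Clast). λz cancels, so Vz/f no longer depends on the elimination rate at all.

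**6. The 20% rule.** In the step 2 example the true extrapolated share is 0.5% to 1.4%.
- If the share is computed as (AUC0-inf − AUClast)/AUC0-inf, the printed form gives −106%, −37%, −3% and +31% at 20, 30, 40 and 60 min. A profile is wrongly flagged when 1 − 1000λz/1010 exceeds 0.20, that is λz below 0.808 per h, or a half-life above about 51.5 min.
- If it is computed as (Clast/λz)/AUC0-inf, the printed form gives 10/1010 = 1.0% at every half-life, and nothing is flagged.

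**The case against.** The strongest reply is that nobody will code this cell. SAP 6 assigns PK to WinNonlin, 12.1 describes the parameters as non-compartmental estimates, and the MRT row takes AUMCinf from that software. The 20% rule also shows what was meant. On this view the slip stays on paper. It does make harm conditional on someone programming, checking or reporting from the SAP text. It does not make the entry right. The SAP defers to WinNonlin by name for AUMCinf but prints its own rule for AUC0-inf, and a checker working from the SAP would either repeat the error or raise a false discrepancy.

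Second, the magnitude is illustrative. That stands: the range of 0.48 to 1.44 rests on assumed half-lives and on hours. The shell supports hours, but the AUC intervals are named in minutes and Listing 16.2.5.6 heads elapsed time in minutes.

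Third, the error would often show itself, through an AUC0-inf below AUC0-t in the same table or a tens-fold discrepancy. That is fair for many cases. It is less so for half-lives somewhat above 41.6 min in hours, where the wrong value exceeds AUClast and looks plausible.

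Fourth, the unit entries in the Table 14.2.4.7 shell ("CL/f (unit) | Vz/f (unit) | MRT (unit")) are template placeholders, and 12.4 already expresses the extrapolated share as a percentage of AUCinf. I agree that these are missing detail and not errors. The point does not depend on them.

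**Conclusion.** The AUC0-inf entry in SAP 12.1 is wrong as printed. This follows from the units alone and needs no assumption about the data. Taken literally, it gives wrong values for AUC0-inf, CL/f, Vz/f and MRT, with MRT affected only through its denominator. With time in hours and terminal half-lives of 20 to 60 min (assumed), AUC0-inf is off by a factor of about 0.48 to 1.44; in minutes the simulated profiles give 29 to 83. Whether this reaches the report depends on whether the printed rule or the software's own output is used, and the SAP does not say which prevails. AUC0-30min, AUC0-300min, AUC0-t, Cmax, Tmax, λz, t½ and the primary glucose endpoint are unaffected. It should be fixed before the PK analysis is programmed, but it does not threaten the trial's main result.

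**What to change.** In the AUC0-inf row of SAP 12.1, replace the calculation with AUC0-inf = AUClast + (Clast_obs/λz). The CL/f, Vz/f and MRT rows then need no change.

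Three optional clarifications could go in at the same time:
- Define percent extrapolated in 12.4 as 100 × (Clast_obs/λz)/AUC0-inf.
- State that the matching WinNonlin AUCinf output is the value used for CL/f, Vz/f and MRT.
- Fill the unit placeholders in Table 14.2.4.7 with one consistent time unit.

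The cost is one line of SAP text, plus a definition, a sentence and a few table headers if the options are taken. Nothing changes in data collection or design.
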